7.7 Patient Follow-up After Completion of WBI

All eligible patients will enter the observation phase of this trial after completion of WBI (see test schedule, Section 4.0). At the follow-up visits, patients will complete a symptom survey and undergo a physical examination. The breast lymphedema symptom survey will assess breast heaviness, swelling, redness, and discomfort. The physical examination will assess the presence or absence of breast edema, which will combine with the symptom score to define cases of breast lymphedema. Lymphedema should be graded using CTCAE version 4.0 (see Section 10.51).

8.0 Dosage Modification Based on Adverse Events

8.1 No Expected Adverse Events

There are no expected adverse events from surgery beyond those related to the standard breast cancer surgery.

8.2 Dose Modifications as per Standard Institutional Practice

Dose modifications for adverse events occurring during physician's choice of adjuvant hormonal or chemotherapy will be managed according to the physician's standard institutional practice.

8.3 Table of Modification of WBI Schedule Based on Adverse Events

ALERT: *ADR reporting may be required for some adverse events (See Section 10)*

Use the NCI Common Terminology Criteria for Adverse Events (CTCAE) version 4.0* unless otherwise specified		
System Organ Class (SOC)	ADVERSE EVENT	ACTION
Injury, poisoning and procedural complications	Dermatitis radiation, grade 3	Hold WBI treatment for one week or until skin reaction improves to < grade 3.
Any hematologic or non-hematologic adverse event	≥ grade 4	Report to the principal investigator at the time of occurrence.

* Located at http://ctep.cancer.gov/protocolDevelopment/electronic_applications.ctc.htm

9.0 **Ancillary Treatment/Supportive Care**

Patients should receive full supportive care while on this study according to institutional standard of care. This includes blood product support, antibiotic treatment, and treatment of other newly diagnosed or concurrent medical conditions.

10.0 **Adverse Event (AE) Reporting and Monitoring**

10.1 Adverse Event Characteristics

CTCAE term (AE description) and grade: The descriptions and grading scales found in the revised NCI Common Terminology Criteria for Adverse Events (CTCAE) version 4.0 will be utilized for AE reporting. However, CTCAE version 5.0 must be used for serious AE reporting through CTEP-AERS as of April 1, 2018. All appropriate treatment areas should have access to a copy of the CTCAE version 5.0. The CTCAE is available at [REDACTED] All reactions determined to be “reportable” in an expedited manner must be reported using the Cancer Therapy Evaluation Program Adverse Event Reporting System (CTEP-AERS), accessed via the CTEP website, [REDACTED] Attribution to protocol treatment for each adverse event must be determined by the investigator and reported on the required forms. Please refer the NCI Guidelines: Adverse Event Reporting Requirements for further details on AE reporting procedures. CTEP-AERS reports should be submitted electronically.

10.11 Adverse Event Monitoring, Data Collection and Reporting

Adverse event monitoring, data collection and reporting, which are required as part of every clinical trial are done to ensure the safety of patients enrolled in the studies as well as those who will enroll in future studies using similar agents. Adverse events are reported in a routine manner at scheduled times during the trial using Medidata Rave. Additionally, certain adverse events must be reported in an expedited manner for timelier monitoring of patient safety and care. Following sections provide information about expedited reporting.

First, identify and grade the severity of the event using the CTCAE version 4.0. Next, determine whether the event is expected or unexpected (see Section 10.2) and if the adverse event is related to the medical treatment or procedure (see Section 10.3). With this information, determine whether the event must be reported as an expedited report (see Section 10.4). **Important:** Expedited adverse event reporting requires submission of a CTEP Adverse Event Reporting System (CTEP-AERS) report(s). Expedited reports are to be completed using CTCAE version 5.0, within the timeframes and via the mechanisms specified in Section 10.4 and 10.5. All AEs reported via expedited mechanisms must also be reported via the routine data reporting mechanisms defined by the protocol (see Sections 10.4 and 18.0).

10.12 CTCAE and Grade

Each CTCAE term in the current version is a unique representation of a specific event used for medical documentation and scientific analysis and is a single MedDRA Lowest Level Term (LLT). Grade is an essential element of the Guidelines and, in general, relates to **severity** for the purposes of regulatory reporting to NCI.

NOTE: A severe AE, as defined by the above grading scale, is **NOT** the same as serious AE which is defined in the table in Section 10.4.

10.2 Expected vs. Unexpected

- The determination of whether an AE is expected is based on the treatment-specific information provided in Section 15.0 of this protocol.
- Unexpected AEs are those not listed in the treatment-specific information provided in Section 15.0 of this protocol.

NOTE: “Unexpected adverse experiences” means any adverse experience that is neither identified in nature, severity, or frequency of risk in the information provided for IRB review nor mentioned in the consent form.

10.3 Assessment of Attribution

When assessing whether an adverse event is related to a medical treatment or procedure, the following attribution categories are utilized:

- Definite – The adverse event *is clearly related* to the agent(s).
- Probable – The adverse event *is likely related* to the agent(s).
- Possible – The adverse event *may be related* to the agent(s).
- Unlikely – The adverse event *is doubtfully related* to the agent(s).
- Unrelated – The adverse event *is clearly NOT related* to the agent(s).

Events determined to be possibly, probably or definitely attributed to a medical treatment suggest there is evidence to indicate a causal relationship between the treatment and the adverse event.

10.31 Special Situations for Expedited Reporting

An expedited report is not required for a specific protocol where an AE is listed as expected. These events must still be reported via routine reporting as specified in Section 10.5. The protocol-specific guidelines supersede the NCI Adverse Event Reporting Guidelines (See Section 10.4) for AE reporting.

10.32 Persistent or Significant Disabilities/Incapacities

Any AE that results in persistent or significant incapacity or substantial disruption of the ability to conduct normal life functions (formerly referred to as disabilities), congenital anomalies, or birth defects, must be reported via CTEP-AERS if they occur at any time following treatment since they are considered to be a serious AE and must be reported to the sponsor as specified in 21 CFR 312.64(b).

10.33 Death

Reportable categories of Death

- Death due to progressive disease should be reported as grade 5 “Disease progression” in the system organ class (SOC) “General disorders and administration site conditions.” Evidence that the death was a manifestation of underlying disease (e.g., radiological changes suggesting tumor growth or progression: clinical deterioration associated with a disease process) should be submitted.
- Any death occurring within 30 days of the last dose, regardless of attribution to the investigational agent/intervention requires expedited reporting within 24 hours.
- Any death occurring greater than 30 days after the last intervention requires expedited reporting within 24 hours only if it is possibly, probably, or definitely related to the intervention.
- When submitting CTEP-AERS reports for “Pregnancy”, “Pregnancy loss”, or “Neonatal loss”, the Pregnancy Information Form should be completed and submitted, along with any additional medical information (form is available on the CTEP website at <http://ctep.cancer.gov/>). The potential risk of exposure of the fetus to the investigational agent(s) or chemotherapy agent(s) should be documented in the “Description of Event” section of the CTEP-AERS report.
- In CTCAE v5.0, pregnancy loss is defined as “Death in utero,” and any pregnancy loss should be reported expeditiously as Grade 4 “Pregnancy loss” under the Pregnancy, puerperium and perinatal conditions SOC. A pregnancy loss should NOT be reported as a Grade 5 event under the Pregnancy, puerperium

and perinatal conditions SOC as currently CTEP-AERS recognizes this event as a patient death.

- A neonatal death should be reported expeditiously as Grade 4, “Death neonatal” under the General disorders and administration SOC.

10.34 Secondary Malignancy

All new malignancies must be reported via CTEP-AERS whether or not they are thought to be related to either previous or current treatment. All new malignancies should be reported, i.e. solid tumors (including non-melanoma skin malignancies), hematologic malignancies, myelodysplastic syndrome/acute myelogenous leukemia, and in situ tumors. In CTCAE v5.0, secondary malignancies may be reported as one of the following three options: 1) Leukemia secondary to oncology chemotherapy, 2) Myelodysplastic syndrome, or 3) Treatment-related secondary malignancy. Whenever possible, the CTEP-AERS reports for new malignancies should include tumor pathology, history or prior tumors, prior treatment/current treatment including duration, any associated risk factors or evidence regarding how long the new malignancy may have been present, when and how the new malignancy was detected, molecular characterization or cytogenetics of the original tumor (if available) and of any new tumor, and new malignancy treatment and outcome, if available.

10.35 Second Malignancy

- A second malignancy is one unrelated to the treatment of a prior malignancy (and is NOT a metastasis from the initial malignancy). Second malignancies require ONLY routine reporting via CDUS.

10.4 Expedited Reporting Requirements: Studies using Commercial Agent(s) ONLY:

Expedited Reporting Requirements for Adverse Events that Occur in a Non-IND/IDE trial within 30 Days of the Last Administration of a Commercial Agent^{1,2}**FDA REPORTING REQUIREMENTS FOR SERIOUS ADVERSE EVENTS (21 CFR Part 312)**

NOTE: Investigators **MUST** immediately report to the sponsor (NCI) **ANY** Serious Adverse Events, whether or not they are considered related to the investigational agent(s)/intervention (21 CFR 312.64)

An adverse event is considered serious if it results in **ANY** of the following outcomes:

- 1) Death
- 2) A life-threatening adverse event
- 3) An adverse event that results in inpatient hospitalization or prolongation of existing hospitalization for \geq 24 hours
- 4) A persistent or significant incapacity or substantial disruption of the ability to conduct normal life functions
- 5) A congenital anomaly/birth defect.
- 6) Important Medical Events (IME) that may not result in death, be life threatening, or require hospitalization may be considered serious when, based upon medical judgment, they may jeopardize the patient or subject and may require medical or surgical intervention to prevent one of the outcomes listed in this definition. (FDA, 21 CFR 312.32; ICH E2A and ICH E6).

ALL SERIOUS adverse events that meet the above criteria **MUST** be immediately reported to the NCI via CTEP-AERS within the timeframes detailed in the table below.

Hospitalization	Grade 1 Timeframes	Grade 2 Timeframes	Grade 3 Timeframes	Grade 4 & 5 Timeframes
Resulting in Hospitalization \geq 24 hrs		7 Calendar Days		24-Hour 3 Calendar Days
Not resulting in Hospitalization \geq 24 hrs	Not required		7 Calendar Days	

Expedited AE reporting timelines are defined as:

- “24-Hour; 3 Calendar Days” – The AE must initially be reported via CTEP-AERS within 24 hours of learning of the AE, followed by a complete expedited report within 3 calendar days of the initial 24-hour report.
- “7 Calendar Days” – A complete expedited report on the AE must be submitted within 7 calendar days of learning of the AE

¹Serious adverse events that occur more than 30 days after the last administration of investigational agent/intervention and have an attribution of possible, probable, or definite require reporting as follows:

Expedited 24-hour notification followed by complete report within 3 calendar days for:

- All Grade 4, and Grade 5 AEs

Expedited 7 calendar day reports for:

- Grade 2 adverse events resulting in hospitalization or prolongation of hospitalization
- Grade 3 adverse events

² For studies using PET or SPECT IND agents, the AE reporting period is limited to 10 radioactive half-lives, rounded UP to the nearest whole day, after the agent/intervention was last administered. Footnote “1” above applies after this reporting period.

Effective Date: May 5, 2011

In the rare occurrence when Internet connectivity is lost, a 24-hour notification is to be made to CTEP by telephone at [REDACTED]. Once Internet connectivity is restored, the 24-hour notification phoned in must be entered electronically by the original submitter at the site.

10.5 Other Required Expedited Reporting

EVENT TYPE	REPORTING PROCEDURE
Other Grade 4 or 5 Events and/or Any Hospitalizations During Treatment Not Otherwise Warranting an Expedited Report	
NCCTG institutions only: Complete a Notification Form: Grade 4 or 5 Non-AER Reportable Events/Hospitalization Form within 5 working days of the date the clinical research associate (CRA) is aware of the event(s) necessitating the form.
 
If a CTEP-AERS report has been submitted, this form does not need to be submitted.

10.51 Adverse Events and Symptoms/Conditions to be Graded at Baseline

Adverse events to be graded at each evaluation and pretreatment symptoms/conditions to be evaluated at baseline per CTCAE v4.0 grading unless otherwise stated in the table below:

System Organ Class (SOC)	Adverse event	Baseline	Each evaluation post-surgery	Each evaluation post WBI
Infections and infestations	Wound Infection		X	X
Injury, poisoning and procedural complications	Dermatitis radiation			X
	Postoperative hemorrhage		X	
	Seroma		X	X
Vascular disorders	Lymphedema	X	X	X

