10.52 Adverse Event Submission Using Case Reports Forms (CRFs)

Submit via appropriate Alliance Case Report Forms (i.e., paper or electronic, as applicable) the following AEs experienced by a patient and not specified in Section 10.51:

- 10.521 Grade 2 AEs deemed *possibly, probably, or definitely* related to study surgery or radiation.
- 10.522 Grade 3 and 4 AEs regardless of attribution to study surgery or radiation.
- 10.523 Grade 5 AEs (Deaths)
 - 10.5231 Any death within 30 days of the patient's last study treatment or procedure regardless of attribution to study surgery or radiation.
 - 10.5232 Any death more than 30 days after the patient's last study treatment or procedure that is felt to be at least possibly study related must also be submitted as a Grade 5 AE, with a CTCAE type and attribution assigned.

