15.0 Whole Breast Irradiation (WBI) Risks

15.1 Risks and Side Effects Related to the Whole Breast Irradiation (WBI)

Risks and side effects related to the WBI include the following:

Likely (*Events that occur more than 10 % of the time*)

- Reddening of the skin during treatment and for several weeks following treatment
- Tanning of the skin lasting months and may be permanent
- Slightly smaller breast size or change in the way the breast looks
- Tiredness and weakness during treatment and for several weeks following treatment
- Muscles in chest wall under treated breast may feel tight or sore
- Swelling of breast

Less Likely (*Events that occur 3 to 9 % of the time*)

- Peeling of the skin in the area treated with radiation
- Pain at the site of radiation treatment

Rare but serious (*Events that occur < 3 % of the time*)

- Cough
- Difficulty breathing
- Irritation of the sac surrounding the heart
- Inflammation of the heart muscle
- Rib fracture
- Another cancer due to radiation therapy

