(Compliance with Test Schedule Section 4.0)

	Surgery Phase	At completion of adjuvant chemotherapy (if applicable)	At completion of WBI	Observation post WBI follow-up
Patient Status: Treatment (Intervention)	X ¹			
Surgery	X ¹			
Contralateral Surgery	X ^{1,9}			
Pathology Information	X			
Adverse Event	X		X ^{4,7}	
Other Adverse Event	X		X ^{7,8}	
Patient Questionnaire: Active Monitoring	X ^{2,3}			X ^{2,3}
Surgeon Questionnaire: Active Monitoring	X ^{2,5}			
Patient Questionnaire: Booklet Compliance	X ¹			X ⁴
Blood Sample Submission: Institution	X ¹			
Tissue Sample Submission: Institution	X ¹			
Adjuvant Systemic Therapy Evaluation Form		X ⁶		
Radiation Treatment Plan Submission			X ⁷	
Radiation Therapy Information Form			X ⁷	
Start of Adjuvant Endocrine/ Biologic Therapy				X ¹⁷
Patient Status: Clinical Follow Up/Observation Evaluation/Observation				X ¹⁰
Termination of Endocrine Therapy				X ¹¹
Termination of Biologic Therapy				X ¹²
Off Treatment (Completion of WBI)			X	
NCCTG sites only:				
Notification – Grade 4 or 5 Non-AER Reportable Events/Hospitalization			At each occurrence (see Section 10.0)	
Notice of New Primary ¹³		At each occurrence	At each occurrence	At each occurrence
Recurrence Information ¹⁴		X	X	X
Local-Regional Recurrence		X	X	X
Documentation Submission ¹⁵				
Distant Recurrence		X	X	X
Documentation Submission ¹⁶				

Early Termination of Follow-Up

Consent Withdrawal

Lost to Follow-Up

These forms must be completed when the study participant is withdrawing consent for QOL (questionnaires), specimens, clinical follow-up only, or all follow-up or if they have become lost to follow-up. These forms are found in the Add Event dropdown list in Rave. Once added, they will be found in the Early Termination of Follow-Up Folder. **Please note:** If the study participant is refusing further study treatment, document the refusal by completing an Off Treatment Form, not a Consent Withdrawal Form.

1. Submit \leq 30 days following surgery.
2. Patient and surgeon questionnaire booklets must be ordered by the site from the CTSU using the form located on the CTSU website; the forms located in the appendices of the protocol can be downloaded and printed directly from the CTSU website for IRB submission only. Forms used by patients must be ordered from the CTSU.

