3. Patient questionnaire booklets will be administered to patients 5 to 30 days following final surgery (initial post-operative visit); every six months (\pm 1 month) for the first 2 years following completion of WBI; then every year (\pm 2 months) for the next 3 years to assess cosmetic outcome.
4. This form must be completed only if the Patient Questionnaire Booklet contains absolutely NO patient provided assessment information.
5. Surgeon questionnaire booklets will be completed by the patient's surgeon 5 to 30 days following final surgery (initial post-operative visit) to assess cosmetic outcome.
6. Submit \leq 30 days following completion/discontinuation of adjuvant chemotherapy.
7. Submit \leq 30 days following completion/discontinuation of radiation therapy.
8. The Other Adverse Event form is only completed if there are adverse events other than the 'solicited' adverse events.
9. This form is required only if the site indicates on the Surgery form that the patient had surgery to the opposite breast.
10. Complete at each evaluation during observation (See Section 4.0)
11. Complete this form only if patient has ended all adjuvant endocrine therapy.
12. Complete this form only if patient has ended all biologic therapy.
13. If, at any time, the patient has a new primary or contralateral breast disease, complete this form
14. If a recurrence has been reported on the Patient Status form, complete this form
15. If a local-regional recurrence has been reported on the Recurrence Information form, complete this form.
16. If a distant recurrence has been reported on the Recurrence Information form, complete this form.
17. Submit \leq 30 days following start of adjuvant endocrine therapy.

Follow-up Material(s)

CRF	Event Monitoring Phase ¹				
	every 12 months until PD	At PD	After PD every 12 months	Death	New Primary
Patient Status: Survival and Disease Status Follow Up/Event Monitoring	X	X ²	X	X	
Recurrence Information ³		X			
Local-Regional Recurrence Documentation Submission ⁴		X			
Distant Recurrence Documentation Submission ⁵		X			
Notice of New Primary ⁶					At each occurrence

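### Radiation dermatitis is scheduled for grading only at evaluations after WBI, and nothing visible asks for the worst grade during treatment, so peak acute severity may be under-recorded

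*Combined protocol and SAP*

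**What the plan says.** - **Grading times.** The table in section 10.51 has three timing columns: baseline, after surgery and after WBI. Radiation dermatitis is marked only under "Each evaluation post WBI". There is no column for the treatment weeks and no instruction to give the worst grade since the last evaluation.
- **Action during treatment.** For grade 3 radiation dermatitis, section 8.3 says: "Hold WBI treatment for one week or until skin reaction improves to < grade 3".
- **Expected timing.** Section 15.1 lists this among the likely effects: "Reddening of the skin during treatment and for several weeks following treatment".
- **Other events.** Section 10.52 sends related grade 2 events and all grade 3 and 4 events to case report forms, but only those "experienced by a patient and not specified in Section 10.51".
- **Forms.** In the 18.2 timetable, two adverse event forms fall under "At completion of WBI". The Adverse Event form carries footnotes 4 and 7. The Other Adverse Event form carries 7 and 8.
  - Footnote 4: "This form must be completed only if the Patient Questionnaire Booklet contains absolutely NO patient provided assessment information".
  - Footnote 7 sets the submission deadline at "30 days following completion/discontinuation of radiation therapy".
  - Footnote 8: "The Other Adverse Event form is only completed if there are adverse events other than the 'solicited' adverse events".
- **Use of the data.** Radiation-related side effects of WBI with boost are goal 2.26 and a secondary endpoint in 16.2. Section 16.64 assesses their type and severity by CTCAE v4.0.

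**The concern.** Acute radiation dermatitis develops during a course of treatment and then recovers. If the skin is graded for the record only at evaluations after the course, a reaction that peaked earlier can be entered at a partly recovered grade. The plan itself foresees a grade 3 reaction that improves under a hold, and so possibly before any evaluation at which 10.51 requires a grade.

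The trial gives a boost to more than one lumpectomy site or to one large one, and one of its secondary aims is to describe the radiation effects of doing so. Acute skin severity is a direct measure of that. If sites differ in whether they enter the peak grade or the grade on the day, the severity table mixes two quantities. If most enter the grade on the day, it understates the reaction.

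**Working it through.** The plan states no dermatitis rate and no figure to reproduce. The check is a reading of the schedule, followed by the direction of any error.

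**1. Is there time for a peak before the first required grade?** Doses are from 7.661 and 7.662, five fractions a week, with the boost in 2 Gy fractions.

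| Whole breast | Boost | Fractions | Weeks |
|---|---|---|---|
| 46 Gy / 2 = 23 | 14 Gy / 2 = 7 | 30 | 6.0 |
| 50 Gy / 2 = 25 | 10 Gy / 2 = 5 | 30 | 6.0 |
| 45 Gy / 1.8 = 25 | 16 Gy / 2 = 8 | 33 | 6.6 |
| 50.4 Gy / 1.8 = 28 | 10 Gy / 2 = 5 | 33 | 6.6 |

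Treatment lasts about 6 to 6.6 weeks before any hold. Section 8.3 provides for grade 3 dermatitis to arise and improve within that time. The documents do not say how often this happens.

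**2. Does another route record the peak?**
- *Section 10.52, including the grade 3 and 4 rule:* no. It excludes events listed in 10.51, and dermatitis is listed.
- *Other Adverse Event form:* no. Footnote 8 keeps it for unsolicited events.
- *Expedited reporting:* not dependably. Section 10.31 waives it for events listed as expected and returns them to routine reporting under 10.5, which contains 10.51 and 10.52.
- *Report to the principal investigator in 8.3:* only from grade 4.
- *Radiotherapy record in 7.69a2:* it covers prescription and doses, not skin grade.
- *Table 4.1:* footnote 7 ties recording to surgery and the 30 days after the last operation. The adverse event row has a second mark, but its column cannot be fixed in the text as read, so it is counted neither way.
- *Adverse Event form at completion of WBI:* this is the remaining route. It takes solicited events, but no visible text says whether it wants the peak grade or the grade on the day.

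**3. Are the footnotes on that form consistent?** Footnote 4 makes completion depend on a blank patient booklet. Booklets are scheduled 5 to 30 days after final surgery and then from six months after WBI, so none is scheduled at completion of WBI. Footnote 4 also sits on the Booklet Compliance row in the observation column, where it makes sense. Footnote 7 requires the Adverse Event form within its deadline, without condition. The two conflict on one cell.

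**4. Direction of the error.** Let P be a woman's highest grade from the start of WBI to the first evaluation after it, and E her grade at that evaluation. Then E ≤ P, with equality only if the peak is still present at that evaluation. For any grade k, the proportion with E ≥ k cannot exceed the proportion with P ≥ k. If p is the true proportion reaching grade k and f the share of those women still at grade k or above when graded, the recorded proportion is p × f, which lies between 0 and p. The documents give neither p nor f.

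**5. A second chance to record?** Observation visits are six-monthly from the end of WBI (4.1, footnote 16). After the end-of-WBI evaluation, the next scheduled visit is about six months later.

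**The case against.** The strongest reply is that the gap is one of wording and that collection may be sound in practice.

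- The case report forms are not in the documents, and 10.53 points to a forms packet that cannot be seen. Section 18.2 defines the WBI phase from the evaluation before treatment to the evaluation after it. A form due at the end of that phase may already ask for the maximum grade.
- Performance status is assessed at the end of WBI, so there is a contact then. Section 15.1 says reddening continues for weeks after treatment, so many reactions would still be visible.
- Section 8.3 presupposes that sites grade the skin during WBI. A hold should leave a trace in the daily dose record, which could be queried against site notes.
- The endpoint is descriptive and secondary, with no test attached.

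All of this stands as a limit on the conclusion. It does not close the gap: nothing visible tells sites to enter the peak, and a dose record shows at most an interruption, not a grade.

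A reader might go further and take footnote 4 literally, inferring that WBI adverse event forms exist only for women who left the booklet blank. The documents do not support that. Footnote 7 requires the same form, no booklet is due at that point, and footnote 8 presupposes that solicited events are recorded elsewhere. Footnote 4 is best read as a misplaced cross-reference.

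**Conclusion.** The point holds as a possible under-recording. As written, the schedule asks for dermatitis grades only after WBI, the other written routes exclude dermatitis or do not dependably record its grade, and the form that should carry it has contradictory footnotes. Peak acute grade may be understated or recorded differently between sites, so the severity reported for goal 2.26 and section 16.64 may be biased low.

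The direction follows from E ≤ P. It rests on the assumption that at least some sites enter the grade on the day. The size cannot be stated, because the documents give neither a dermatitis rate nor the share of reactions that improve before grading. The range in section 15.1 for skin peeling is not a rate of grade 3 dermatitis and should not be used as one.

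A reader might infer that acute reactions are lost, or that the worst grade was never collected. That goes too far: the forms are unseen, an evaluation follows WBI, and 10.52 still collects other acute radiation events (related grade 2, and all grade 3 and 4). The primary endpoint is not affected.

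**What to change.** - **Section 10.51:** define the radiation dermatitis entry as the maximum CTCAE v4.0 grade from the start of WBI to the first evaluation after WBI, and at later evaluations as the maximum since the previous one. Record the first on the existing Adverse Event form at completion of WBI.
- **Section 16.64:** state that this maximum grade is what is tabulated.
- **Section 18.2:** remove footnote 4 from the Adverse Event row and keep footnote 7.

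The cost is one field definition, slightly more abstraction from site notes and one deleted footnote number. No visit, form or treatment rule changes, and 8.3 already presupposes that the skin is graded during WBI. If the unseen form already asks for the maximum, the change only brings the protocol text into line with it.
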